10.1.2 Reference Day and Study Day

The reference day (Day 1) will be the day of the first dose of study drug administration.

For a patient who was randomized but not exposed, the reference day date will be imputed by the randomization date.

The reference day for Period 1 (Period 1 Day 1) will be the reference day.

The reference day for Period 2 (Period 2 Day 1) will be the first day of IMP administration during Period 2. For a patient who entered the second period but was not exposed during this period, this reference day date will be imputed by the date of Visit 6 IRT call, if any, or the Visit 6 date.

The study day is defined relative to the reference day date. For assessments that occur after this visit date, the study day is calculated as (assessment date – reference day date + 1). For assessments that occur prior to first dose date, study day will be calculated as (assessment date – reference day date).

For the analyses being done by treatment arm, an **analysis day** will need to be derived for each treatment period as described in [Table 10.1-1](#). The analysis day is defined relative to the date of reference day of each study period.

For assessments that occur prior to reference day date, analysis day will be calculated as (assessment date – reference day date);

For assessments that occur on or after the Period 1 reference day date until the end of the wash-out period, analysis day will be calculated as (assessment date – Period 1 reference day date +1);

For assessments that occur on or after Period 2 reference day date the analysis day will be calculated as (assessment date – Period 2 reference day date +1);

Thus, there is no study day or analysis day referring to Day 0.

10.1.3 Target Days and Visit Window

Visit windows are summarized in [Table 10.1-3](#) for efficacy data and urine drug screen collection and, in [Table 10.1-2](#) for all other safety endpoints.

When there are multiple observations within a visit window, the value closest to the target day will be analyzed (as described in [Table 10.1-1](#)).

For safety assessments, on-treatment assessments will be preferred to off-treatment ones.

In case of ties between observations located on different sides of the target, the observation with the earliest date/time will be used. In case of ties between observations located on the same side of the target, (i.e., more than one value for the same day but at different time), the observation with the earliest date/time will be used. However, in case of non-respect of wash-out period, the one done at least 7 days after last Period 1 dosing date will be preferred.

For efficacy, PRO endpoints visit windowing will apply whether patient is on or off treatment.

Table 10.1-1 Longitudinal Assessment – Analysis Day and Target Day

Treatment Period	Visit / Day	Analysis visit	Target Day (defined by period)	Observation used for analysis, if more than one exists
Screening	Visit 1 / Day -28 to -1	Screening	Day -28 to -1	Latest value
Period 1	Visit 2 / Day 1	Day 1	Day 1*	Closest to Target Day But Day 1 H0 should be before 1 st IMP intake and D1H3 should be post IMP intake
	Visit 3 / Day 8	Day 8	Day 8	Closest to Target Day
	Visit 4 / Day 15	Day 15	Day 15	Closest to Target Day
	Visit 5 / D21	D21	D21	Closest to Target Day
Period 2	Visit 6 / Day 31	Day 1	Day 1*	Closest to Target Day But Day 1 H0 should be before 1 st IMP intake and

Treatment Period	Visit / Day	Analysis visit	Target Day (defined by period)	Observation used for analysis, if more than one exists
				D1H3 should be post IMP intake.
	Visit 7 / Day 38	Day 8	Day 8	Closest to Target Day
	Visit 8 / Day 45	Day 15	Day 15	Closest to Target Day
	Visit 9 / Day 51	D21	D21	Closest to Target Day
Follow-up	Visit 10 / Day 58	Day 28	Day 28**	Closest to Target Day

H = Hours; IMP = Investigational medical product.

** Day 1 is based on the date of IRT call within each period*

*** Day 28 relative to the period where IMP is permanently discontinued thus visit is expected between Day 25 and Day 31*

Table 10.1-2 Longitudinal Assessment – Target Day and Visit Window – Part 1

Treatment Period	Visit / Day	Physical examination / 12-lead ECG / Clinical laboratory blood sampling	Target Day (defined by period)	Examination of oral mucosa / C-SSRS	Body weight / Serum urine pregnancy test	Vital signs	Dipstick urine
Screening	Visit 1 / Day - 28 to -01	Day 28 – D1H0	Day 28 to -01	Day 28 to -01	Day 28 to -01	Day 28 to -01	Day 28 – D1H0 (before 1st IMP dosing)
Period 1	Visit 2 / Day 1H0	Day 1*	Day 1H0 *	Day 1H0 (before P1 IMP intake)	Day 1 H0 (before P1 IMP intake)	Day 1 H0 (before P1 IMP intake)	Day 1 post dose (the day of 1st P1 IMP intake)
	Visit 2 / Day 1	Day 1 H2- H4*					Day 2 (day following IMP intake) – Day 18
	Visit 4 / Day 15	Day 15		Day 1 post dose to Day 18			Day 19 to LP1V
	Visit 5 / D21	D21	Day 1 post dose to LP1V	Day 19 to LP1V			
	Wash-out						
Period 2	Visit 6 / Day - 31	Day 1H0*		Day 1 – 4 days to D1H0 *	D1H0 (before P2 IMP intake)	Day 1 – 4 days to D1H0	Day 1 post dose (the day of 1st P2 IMP intake)
	Visit 6 / Day - 31	Day 1H2- H4*					Day 2 (day following IMP intake) – Day 18
	Visit 8 / Day 45	Day 15		Day 1 post dose to Day 18			Day 19 to LP2V
	Visit 9 / Day 51	D21	Day 1 post dose to LP2V	Day 19 to LP2V			
	Follow-up	Visit 10 / Day 58	Day 28***		after last IMP dosing	After last IMP dosing	Day 1 post 1st IMP dosing to after last IMP dosing

H = Hour; P = Period; LP1V = Last visit during Period 1, LP2V = Last visit during Period 2, IMP = Investigational Medical Product; IRT = Interactive response technology; ECG = Electrocardiogram; C-SSRS = Columbia-Suicide Severity Rating Scale.

* Day 1 is based on the date of IRT call within each period.

*** Day 28 relative to the period where IMP is permanently discontinued.

Table 10.1-3 Longitudinal Assessment – Target Day and Visit Window – Part 2

Treatment Period	Visit / Day	Target Day (defined by period)	Urine drug screen	11-point NRS spasticity / Daily spasm count	MAS	MSSS-88	T25FW test
Screening	Visit 1 / Day - 28 to -01	Day -28 to -01	Day -28 to -01	Day -28 to -01	Day -28 to -01		
Period 1	Visit 2 / Day 1H0	Day 1*	Day 1 H0 (before P1 IMP intake)	Day1H0 (before P1 IMP intake)*	Day1H0 (before P1 IMP intake)	Day 1H0 (before P1 IMP intake)	Day 1H0 (before P1 IMP intake)
	Visit 2 / Day 1	Day 1 H2- H4**			Day1 post dose (the day of 1 st P1 IMP intake)** up to Day 18		
	Visit 4 / Day 15	Day 15		Day 2 (day following IMP intake) – Day 18 (or the first day of maintenance phase)			
	Visit 5 / D21	D21***		Day 19 up to LP1V	Day 19 up to LP1V	Day 1 post dose of 1 st IMP intake up to LP1V	Day 1 post dose of 1 st IMP intake up to LP1V
Wash out period							
Period 2	Visit 6 / Day 31	Day 1H0*		Day 1 – 4 days to D1H0 *	Day 1H0 (before P2 IMP intake)	Day 1H0 (before P2 IMP intake)	Day 1H0 (before P2 IMP intake)
	Visit 6 / Day 31	Day 1H2- H4**			Day 1 post dose (the day of 1 st P2 IMP intake)** up to Day 18		
	Visit 8 / Day 45	Day 15		Day 2 (day following IMP intake) – Day 18 (or the first day of maintenance phase)			
	Visit 9 / Day 51	D21***		Day 19 to LP2V	Day 19 to LP2V	Day 1 post dose of Period 2 1 st IMP intake up to LP2V	Day 1 post dose of Period 2 1 st IMP intake up to LP2V
Follow-up	Visit 10 / Day 58	Day 28****		After last IMP dosing			

H = Hours, P = Period; LP1V = Last visit during Period 1, LP2V = Last visit during Period 2, IMP = Investigational Medicinal Product, NRS = Numerical Rating Scale; IRT = Interactive Response System, MAS = Modified Ashworth Scale, MSSS-88 = Multiple Sclerosis Spasticity Scale; T25FW = Timed 25-Foot Walk.

* Day 1 is based on the date of IRT call within each period.

** D1H2-H4 for sensitivity analysis purpose only assessments collected between at H3 (+/- 15 min) post first IMP morning spray will be considered. Should be collected during the titration phase

*** D21 should be collected during the maintenance phase (including off-treatment days).

**** Day 28 relative to the period where IMP is permanently discontinued.

For patient electronic diary-based endpoints (NRS-spasticity and spasm count), baseline is defined as the weekly average of daily electronic diary entries over the last 7 days prior to randomization (Visit 2, Period 1 Day 1H0).

In case of missing assessments within the 7 days preceding Period1 Day1 H0

- For 11-point NRS spasticity scale, the weekly average will be set to missing if scores are missing for 4 days in total or for 3 consecutive days within the 7-days period.
- For daily spasm count, the weekly average will be derived as detailed in [Section 10.19](#) and will be set to missing if spasm count is not collected during 4 days out of 7 or for 3 consecutive days during the last 7 days preceding Day 1H0.

For clinic-efficacy based endpoints, baseline is defined as the last record or measure collected prior to the first dose of IMP in each treatment period.

However, if deemed necessary the baseline will be defined for each period as described in [Section 10.1.2](#) as:

- the reference day for Period 1,
- the reference day for Period 2,

For clinic-safety based endpoints, baseline is defined as the last record or measure collected prior to the first dose of IMP or if deemed necessary as the reference day as described in [Section 10.1.2](#).

10.3 Change from Baseline

Change from baseline (CFB) will be calculated as:

$$(\text{post-baseline} - \text{baseline}).$$

CFB will be calculated for patients with both a baseline and post-baseline value as applicable.

10.4 Percentage Change from Baseline

Percent CFB will be calculated, where applicable, as:

$$(\text{CFB}/\text{baseline}) * 100.$$

If a baseline value has not been recorded for a parameter, then percent CFB will be missing for that parameter.

If baseline and post baseline are rates the following formula will be used:

$$((\frac{\text{Post baseline score}/\text{count} * \text{baseline duration}}{\text{Baseline score}/\text{count} * \text{post baseline duration}} - 1) * 100)$$

10.5 Time Conversion

Time conversion will follow the rules described below:

- 1 week = 7 days,
- 1 Month = 30.4375 days,
- 1 year = 365.25 days.

10.6 Patient Disposition

The time to treatment discontinuation expressed in day is defined as:

- the date of last administration – the date of 1st IMP spray intake +1 day.

The time to study discontinuation expressed in day is defined as:

- End of study day – date of randomization + 1 day.

Where the date of the 1st IMP spray intake (e.g., IMP start date) will be retrieved from the eCRF “PK sample collection form” and, if missing, from the eDiary first spray date for Period 1 whereas, the end of treatment date will be the latest date between the end of treatment date coming from eCRF “End of treatment Period 1” form and “End of treatment Period 2” form.

Censoring rules for time to event analysis are defined in [Section 12.1](#).

10.7 Duration of Treatment

The duration of study drug exposure expressed in days will be defined for each study drug as:

- the date of last administration – the first day of administration +1 day.

The mean duration of study drug exposure expressed in patient-time will be defined as follows:

- The mean duration (patient-year) = $(\sum_{i=1}^{i=n} D_i) / 365.25$
- The mean duration (patient-week) = $(\sum_{i=1}^{i=n} D_i) / 7$

With n being the number of patients within the Safety Analysis Set and i=1,2, 3,...,n, and, with Di being the duration of treatment (in days) for patient i.

The IMP start date will be retrieved from the eCRF “PK sample collection form” for each treatment period whereas the end of treatment date for each period will respectively be coming from eCRF “End of treatment Period 1” form and “End of treatment Period 2” form. However, if the information is missing on the eCRF “PK sample collection”, the first IMP spray date will be retrieved from the eDiary first spray date of each treatment period.

10.8.1 Study Phases Start and Stop Dates used to summarize IMP Dosing

The titration phase

- Start of the titration phase during Period 1 is defined as:

$$\text{Min}(\text{randomization date, 1st IMP dosing date})$$
- Start of the titration phase during Period 2 is defined as:

$$\text{Min}(\text{the date of IRT call for Period 2, Visit 6 date})$$
- End of the titration phase during Period 1 is defined as:

$$\text{Min}(\text{the day preceding Visit 4 date, the last dose date during Period})$$
- End of the titration phase during Period 2 is defined as:

$$\text{Min}(\text{the day preceding Visit 8 date, the last dose date during Period 2})$$

The maintenance phase

- Start of the maintenance phase during Period 1 is defined as:

$$\text{the date of Visit 4,}$$
- Start of the maintenance phase during Period 2 is defined as:

$$\text{the date of Visit 8,}$$
- End date of the maintenance phase during Period 1 is defined as:

$$\text{Min}(\text{Visit 5 date, the date of the last dose of study drug})$$

- End date of the maintenance phase during Period 2 is defined as:
the date of the last dose of study drug

10.8.2 Number of Sprays Summary

For each parameter presented in this section,

- **The start and stop date** of each studied period is defined in [Section 10.8.1](#). These studied periods are defined for Period 1 and Period 2 to allow summaries by treatment arm.
- **The duration of each studied period** will then be derived using the appropriate treatment phase (titration, maintenance) for each treatment period as: Date of stop – date of start + 1 day
- eDiary information will be used to retrieve the total daily number of sprays taken by a given patient
- A **non-missing diary day** is defined as any day where the eDiary is filled but IMP dosing information are fully included or partial (missing morning or evening dose) or totally missing.
- A **missing diary day** is defined as any day where the eDiary is not filled
- **Imputation rule:** for a non-missing diary day where IMP dosing information is partial or missing the number of sprays taken on that missing morning or evening administration will be imputed to "0" to derive the total daily number of spray taken.

The mean number of sprays is defined for each treatment arm as the total number of sprays taken during the studied period divided by the number of patients within the studied period regardless intermittent IMP discontinuation.

The patient mean number of daily sprays a patient has taken on a daily basis is calculated for each studied period as the total number of sprays taken divided by the number of non-missing diary days for each patient.

Based on the above the patient mean number of daily sprays (also called mean use of IMP) will also be categorized as follows:

- ≤ 6 sprays,
- > 6 sprays and ≤ 12 sprays,
- > 12 sprays.

The total number of daily sprays is referring to the total number of sprays a patient has taken on a daily basis for a studied period.

The patient median number of daily sprays refers to is referring to the median number of sprays a patient has taken on a daily basis for a studied period.

The patient mode number of daily sprays refers to more frequently occurring number of sprays a patient has taken on a daily basis for a studied period. If a patient has more than one mode or no mode determined then the patient has a 'missing' mode.

The patient maximal number of daily sprays refers to the maximal number of sprays a patient has taken on a daily basis for a studied period.

The patient percentage of imputed diary days is derived for each patients as the number of non-missing diary days where morning and/or evening number of sprays are imputed to '0' to calculate the total daily dose divided by the number of non-missing diary days for a studied period and multiply by 100.

10.9 Compliance

Compliance will be derived, for each patient, during the maintenance phase, based on optimized and amended doses information as reported in the “Dose amendment” eCRF form and the total daily number of sprays derived from the eDiary as the sum of morning and evening number sprays applying missing data rule imputation on non-missing diary days as described in [Section 10.8.2](#).

A compliant day, is defined for each patient as a day when the total number of sprays taken is

- Within +/- 1 (and between 1 and 12) of the patients' optimized dose range as defined in [Table 10.9-1](#) when sprays are taken outside of an amended dose period,
- Equal to the amended dose +/- 1 spray (and between 1 and 12) when sprays are taken between start and stop date of an amended dose period as collected in the eCRF.

The compliance will then be defined as

$$100 * \left(\frac{\text{number of compliant days}}{\text{number of days with non-missing total daily dose information within the study period}} \right)$$

Table 10.9-1 Optimized Daily Dose and Allowed Optimized Dose Range

Optimized dose	Maximal allowed dose	Minimal Allowed dose
1	2	1
2	3	1
3	4	2
4	5	3
5	6	4
6	7	5
7	8	6
8	9	7
9	10	8
10	11	9
11	12	10
12	12	11

The rate of “0” total daily spray is defined at patient level as

$$100 * \left(\frac{\text{number of days with total daily dose= 0}}{\text{study period duration*}} \right)$$

The rate of “> 12” total daily spray is defined at patient level as

$$100 * \left(\frac{\text{number of days with total daily dose is >12}}{\text{study period duration*}} \right)$$

The rate of missing diary day IMP information is defined for each patient as:

$$100 * \left(\frac{\text{number of days with missing diary dosing information}}{\text{study period duration*}} \right)$$

Using missing morning and/or evening number of sprays information from either missing diary day and non-missing diary day (as defined in [Section 10.8.2](#))

* The study period duration refers to either the titration phase duration or the maintenance phase duration for period.

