9.1.2.3 Visit 4 (Day 15) and Visit 5 (Day 21)

Visits 4 and 5 will occur 14 and 20 days after the first dose of IMP, respectively. A visit window of ± 1 and ± 2 days, respectively, from the scheduled visit date is permitted, but it is preferred that the visit is performed on the scheduled visit day, where possible.

Once a stable daily dose has been reached, patients should gradually decrease the interval between sprays to a target interval of approximately 1 minute between sprays. Patients should continue IMP administration at the same dose level achieved at the end of titration (i.e., their daily optimized dose) ± 1 spray divided into a morning dose and an evening dose for approximately 7 days (maintenance-dose phase). Administration of the morning and evening doses of IMP should be maintained around the same time of each day in a consistent manner in relation to food consumption, i.e., within 30 minutes after starting a snack or meal.

On Visit 5, patients will administer their morning dose of IMP with a standardized snack containing at least 300 kcal (of which approximately 30 kcal is composed of fat) at the trial site under the supervision of site staff. The IMP will not be administered in the evening of Visit 5 (Day 21).

The following assessments/procedures will be performed at these visits, unless otherwise indicated:

- MAS assessment (Visit 5 [3 hours ± 15 minutes after the first spray of the morning dose] only)
- T25FW test (Visit 5 only)
- Concomitant medications review
- AE review

- Physical examination (Visit 5 only)
- Examination of the oral mucosa
- Vital signs measurement
- 12-lead ECG (Visit 5 only)
- Clinical laboratory sampling (hematology and biochemistry) (Visit 5 only)
- PK blood sampling for IMP ([Section 9.2.12.1](#))
- MSSS-88 assessment (Visit 5 only)
- C-SSRS assessment
- IMP dosing at the investigational site (Visit 5 [morning] only)
- IMP dispensing (Visit 4 only)
- IMP collection and compliance review ([Section 9.2.16](#))

The exact time of PK blood sampling and the time of the patient's snacks and meals should be recorded.

Patients should be reminded to record their 11-point NRS spasticity score, spasm count, use of antispasticity medications, and IMP dosing in the electronic diary once daily, around the same time each day, preferably in the evening before retiring to sleep.

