9.1.4.3 Visit 8 (Day 45) and Visit 9 (Day 51, End of Treatment)

Visits 8 and 9 will occur 44 and 50 days after the first dose of IMP, respectively. A visit window of ± 1 and ± 2 days, respectively, from the scheduled visit date is permitted, but it is preferred that the visit is performed on the scheduled visit day, where possible.

Once a stable daily dose has been reached, patients should gradually decrease the interval between sprays to a target interval of approximately 1 minute between sprays. Patients should continue IMP administration at the same dose level achieved at the end of titration (i.e., their daily optimized dose) ± 1 spray divided into a morning dose and an evening dose for approximately 7 days (maintenance-dose phase). Administration of the morning and evening doses of IMP should be maintained around the same time of each day in a

consistent manner in relation to food consumption, i.e., within 30 minutes after starting a snack or meal.

On Visit 9, patients will administer the morning dose of IMP with a standardized snack containing at least 300 kcal (of which approximately 30 kcal is composed of fat) at the trial site under the supervision of site staff. The IMP will not be administered in the evening of Visit 9 (Day 51).

The following assessments/procedures will be performed at these visits, unless otherwise indicated:

- MAS assessment (Visit 9 [3 hours ± 15 minutes after the first spray of the morning dose] only)
- T25FW test (Visit 9 only)
- Concomitant medication review
- AE review
- Physical examination (Visit 9 only)
- Examination of the oral mucosa
- Vital signs measurement
- 12-lead ECG (Visit 9 only)
- Clinical laboratory sampling (hematology and biochemistry) (Visit 9 only)
- PK blood sampling for IMP ([Section 9.2.12.1](#))
- MSSS-88 assessment (Visit 9 only)
- C-SSRS assessment
- IMP dosing at the investigational site (Visit 9 [morning] only)
- IMP dispensing (Visit 8 only)
- IMP collection and compliance review

The exact time of PK blood sampling and the time of the patient's snacks and meals should be recorded.

Patients should be reminded to record their 11-point NRS spasticity score, spasm count, use of antispasticity medications, and IMP dosing in the electronic diary once daily, around the same time each day, preferably in the evening before retiring to sleep.

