12.3.1.3 Compliance

Compliance

Based on the total daily number of sprays taken recorded by the patient on the eDiary and on the optimized dose defined at Day 15 of each treatment period and collected on the eCRF "Dose adjustment" form the compliance to study drug will be assessed, during the maintenance phase of each treatment period, by the means of the 4 below parameters:

- The compliance (%),
- The rate of "0 total daily spray (%),
- The rate of "> 12" total daily sprays (%),
- The rate of missing diary day IMP information (%),

which will be summarized by treatment arm.

Detailed calculation along with missing data handling is described in [Section 10.9](#).

Furthermore, the percentage of patients meeting study drug compliance will be presented in the following categories of days in the allowed dose range (coded as yes/no): < 80%, \geq 80% to < 90%, \geq 90% to < 100 % and = 100%.

Additionally, the **patient percentage of imputed diary days** (as defined in [Section 10.8.2](#)) which represents the percentage of days where missing morning and/or evening number of sprays taken have been imputed to '0' to derive the total daily IMP dose and thus compliance is based on imputed total number of sprays taken that day will be described by treatment arm.

Optimized Dose

The optimized dose will be summarized as quantitative and categorical variable per treatment arm. The need of optimized dose adjustment will also be described along with reason for dose adjustment.

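### The compliance rule in SAP 10.9 holds the morning-only last maintenance day to the full daily dose, so fully adherent patients at middle and higher doses are scored below 100%

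*SAP*

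**What the plan says.** **Last dosing day.** Protocol 9.1.2.3 says "The IMP will not be administered in the evening of Visit 5 (Day 21"), and Protocol 9.1.4.3 says "The IMP will not be administered in the evening of Visit 9 (Day 51"). Footnote h of the SAP's own schedule of assessments (SAP 8.1) repeats this for both days.

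**Maintenance phase.** In SAP 10.8.1, "End date of the maintenance phase during Period 1 is defined as" the earlier of "Visit 5 date, the date of the last dose of study drug". "End date of the maintenance phase during Period 2 is defined as" the last dose date. The phase starts at Visit 4 (Period 1) or Visit 8 (Period 2).

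**Compliant day.** SAP 10.9: "A compliant day, is defined for each patient as a day when the total number of sprays taken is" within 1 spray of the optimized dose range in Table 10.9-1, or of an amended dose where one is recorded. The denominator is the number of days with a non-missing total daily dose.

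**Blank entries.** SAP 10.8.2: "for a non-missing diary day where IMP dosing information is partial or missing the number of sprays taken on that missing morning or evening" administration is set to 0.

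**Reporting.** SAP 12.3.1.3: "the percentage of patients meeting study drug compliance will be presented in the following categories", namely below 80%, 80% to below 90%, 90% to below 100%, and exactly 100%.

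**Split of the dose.** Protocol 8.1.2 asks patients on stable dosing to try to balance the morning and evening sprays, and permits the optimized dose ±1 spray/day.

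**The concern.** For an adherent patient the last maintenance day is the Visit 5 or Visit 9 day. About half the daily dose is taken, by design, but the day is compared with the whole daily dose. Leaving the evening entry blank does not remove the day, because the blank becomes 0. The compliance table would then report a scheduled omission as non-adherence, and the category a perfect patient falls in would depend partly on visit timing. A blank evening entry would also add to the imputed-diary-day percentage (10.8.2) and the missing-dosing-information rate (10.9), although no dose was due.

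Appendix 1 of the SAP does recognise the morning-only day: major deviation 12 asks only for a morning spray on the last maintenance day. The absence of any matching provision in 10.9 looks like an oversight.

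**Working it through.** **Step 1. Reproduce Table 10.9-1.** For optimized dose d, minimum = max(1, d − 1) and maximum = min(12, d + 1). All 12 rows match.

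**Step 2. Last-day result.** The patient takes exactly the optimized dose, split as evenly as possible, so morning sprays m = d/2 rounded down or up (dose 1 taken in the morning). The day passes if m is at least the minimum. The last column adds the ±1 again to the tabulated range, which the wording of 10.9 permits (limit = minimum − 1, not below 1).

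| d | m | Table minimum | Passes? | Passes if ±1 is added again? |
|---|---|---|---|---|
| 1 | 1 | 1 | yes | yes |
| 2 | 1 | 1 | yes | yes |
| 3 | 1 or 2 | 2 | only with 2 | yes |
| 4 | 2 | 3 | no | yes (limit 2) |
| 5 | 2 or 3 | 4 | no | only with 3 (limit 3) |
| 6 | 3 | 5 | no | no (limit 4) |
| 8 | 4 | 7 | no | no (limit 6) |
| 10 | 5 | 9 | no | no (limit 8) |
| 12 | 6 | 11 | no | no (limit 10) |

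Doses 7, 9 and 11 fail under both readings.

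**Step 3. Maximum compliance.** Protocol 9.1.2.3 allows Visit 4 on Day 14 to 16 and Visit 5 on Day 19 to 23; Period 2 has the same windows. Phase length L = Visit 5 day − Visit 4 day + 1, and with the last day failing the maximum is (L − 1)/L.

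- On schedule: L = 21 − 15 + 1 = 7, and 6/7 = 85.7%.
- Shortest: L = 19 − 16 + 1 = 4, and 3/4 = 75.0%.
- Longest: L = 23 − 14 + 1 = 10, and 9/10 = 90.0%.

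Of the 3 × 5 = 15 in-window visit-day combinations, only one gives L = 4 and so a result below 80%. L = 5 already gives 4/5 = 80.0%.

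**Step 4. Mean daily sprays.** Mean = ((L − 1)d + m)/L. At d = 12, m = 6:

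- L = 7: (72 + 6)/7 = 11.14, which is 7.1% below 12.
- L = 4: (36 + 6)/4 = 10.5.
- L = 10: (108 + 6)/10 = 11.4.

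At L = 7 the shortfall is 4.8% to 9.5% for doses 2 to 12, and nil for dose 1. Six of the seven days are at d, so the median and mode stay at d.

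**Step 5. Diary on Day 51.** The on-time diary opens at 6:00 pm (SAP 10.15), while the protocol has patients complete the diary until Visit 9 (9.2.14.1). If no diary is filled that evening, Day 51 is a missing diary day and leaves the denominator. The same on-schedule patient then scores 6/7 = 85.7% in Period 1 and 6/6 = 100% in Period 2.

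**Step 6. After the change.** With the last day left out, this patient scores 100% at every dose and the mean equals d (12.0 rather than 11.14). Judging the day against the usual morning dose also gives 100%.

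**The case against.** The strongest reply is that the effect is narrow, conditional and descriptive. Much of that stands.

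- A reader might infer that no adherent patient can reach 100%, or that the top category must be empty. The documents do not support this. Doses 1 and 2 pass, and dose 3 passes with 2 morning sprays. Dose 4 passes with the permitted extra spray: 3 morning + 2 evening, 3 against a minimum of 3. Balance is something patients are asked to attempt, so an uneven split can also pass.
- The wording of 10.9 may add ±1 to a range that already contains it. On that reading failure is certain only from dose 6 for a patient at the optimized dose.
- A Day 51 diary entry is not assured, so 100% may be attainable in Period 2. That answers the ceiling there but leaves the periods measured differently.
- An amended-dose record could in principle cover the day. The case report form is not available here; the protocol and SAP provide for no such entry.
- A reader might infer that the reported mean is wrong. It is a correct average of sprays taken. It is low only as a description of the maintenance dose level, and the optimized dose, median and mode are reported separately.
- Results below 80% need the shortest phase, and the protocol prefers visits on the scheduled day.

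None of this supplies the missing rule for the last day.

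**Conclusion.** The point holds in limited form. As written, SAP 10.8.1 and 10.9 score a fully adherent patient at the optimized dose non-compliant on the Visit 5/Visit 9 day at doses of 4 or more under Table 10.9-1, or 6 or more if the ±1 is added again. This assumes a roughly balanced split, a diary entry for that day and no amended-dose record covering it. Such patients cannot enter the 100% category, and on schedule they fall in the 80% to below 90% band. The documents give no dose distribution, so the share of patients affected cannot be stated.

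A reader might carry this into the efficacy results; the documents do not support that. The primary estimand applies regardless of treatment compliance (SAP Table 9.1-2), and no compliance percentage is among the major deviations in SAP Appendix 1 that determine the per-protocol set. The rule applies in both arms. The split at 6 sprays/day in the dose categories and the safety subgroup is hardly touched: in the cases checked it moves only for dose 7 with 3 morning sprays and a 4-day phase, (21 + 3)/4 = 6.0.

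The SAP should be corrected because the compliance table would otherwise mislead, but nothing confirmatory depends on it.

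**What to change.** In SAP 10.8.1 and 10.9:

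- For compliance, end the window on the day before Visit 5/Visit 9, or on the last dose date if earlier. Alternatively, keep the day and judge its morning dose against the patient's usual morning dose. Use the same rule in both periods.
- Apply the shorter window to the mean daily sprays too, if that mean is meant to describe the maintenance dose level. If it is meant to average sprays taken, leave it and say so.
- Do not count the unscheduled evening dose on that day as imputed or as missing dosing information.
- State whether the ±1 is already included in Table 10.9-1.

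The cost is a few sentences in the SAP and a small programming change. No new data are needed, and neither dosing nor visits change.
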